#### 6.2 RECRUITMENT AND CONSENT

*Phase 1 Manual Development:* No research participants are involved in Phase 1, and so recruitment and consent considerations do not apply.

#### Phase 2b Scoping Study:

For the qualitative interviews that contribute to the phase 2b scoping study our colleagues in the collaborating local authorities and CAMHS teams will contact local authority children's service managers, social workers and CAMHS practitioners by email, providing an information sheet and study contact details for interested parties. VIPP interveners delivering VIPP-FC with other appropriate providers may also be invited to take part in this stage of the study. Foster carers will be contacted through community foster carer groups, to whom information sheets will be distributed. Finally, parents will be approached by the local authorities through their parent liaison groups and provided with an information and study contact details for those interested in taking part.

Information sheets will be provided detailing the qualitative study process and confidentiality arrangements, and written, informed consent will be obtained from all parties prior to interviewing.

#### Phase 2a and Phase 3 (Intervention)

As the recruitment and consent process for the non-randomised pilot case series (Phase 2A) and the pilot RCT (Phase 3) are essentially the same, we describe them together in this section.

#### Screening and identification stage

As noted above, the screening process we envisage will be essential to the success of this project and will depend on an effective collaboration with local authorities, who will send out information sheets, initial consent forms and screening measures to all foster carers in the study localities. In addition, local

authorities will send out a letter to all parents explaining the study and the opting-out process, including contact details of the research team. In Phase 2A we will work with up to two local authorities, and will screen approximately 100 children. In phase 3 we will aim for a minimum screening sample of 500 foster carers from 6-10 local authorities. In both cases, all foster carers or special guardians registered with the local authority caring for children under 7 will be sent an information sheet, screening measures, a consent form and contact details of the research team so that they may ask questions if they wish. Screening measures and completed consent forms will be returned using a pre-paid envelope by foster carers to the University or completed online via study database, Redcap. Letters will also be sent to foster care agencies with information and contact details of the research team that may be given to potential participants registered with these organisations. Where self-referrals are received, foster carers will be asked for the child's social worker's details in order for the local authority to initiate the screening process, including contacting the birth parents. As with the families that are contacted through the local authorities, self-referrals will have the contact details of the research team if they wish to discuss the study in more detail. A minimum two-week period will be given between sending out the letter to parents and initiating the child's participation in the study.

Once initial consent forms (paper and online) and screening measures have been received by the research team, they will contact participants, thanking them for their response and re-iterating the research process. Invitations and follow-up phone calls will be made to all foster carers reporting RAD symptoms over the screening cut-off to take part in a face-to-face interview assessment to confirm eligibility (establishing diagnostic status). This interview would take place at the foster carer's home.

As the screening/identification stage (which consists of a postal and/or an online survey and carer interview) involves no direct contact with the child and involves minimal burden or risk, we will only obtain active consent from the foster carer. However, a letter will be sent to all parents with an explanation of the study and the process of opting-out (except in circumstances where the local authority deems this inappropriate). If after the two-week period for opting-out the Local Authority or the research team has not been contacted by the parent to opt-out, the screening process will be initiated. Foster carers will receive an information sheet explaining the study fully, and a contact telephone number of a member of the research team if they have any questions. The information sheet will explain that completing the screening measures does not entail any obligation to participate in the other stages of the study (the pilot intervention). Written consent will be provided on the consent form (completed by the carer but not a member of the research team at this stage) and posted to the research team along with the screening questionnaires. The study team will receive email notifications from the study database when a participant

gives consent and completes the questionnaires online. Both paper and online consent forms will require the carer to provide their contact details (including the child's initials) in order for the research team to contact them if they meet the screening cut-off. Carers will be given a £10 voucher to thank them for completing the screening questionnaires.

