Phase 2b: Conducting a scoping study with key stakeholders to inform pilot trial design. Delivering interventions and testing their efficacy is inevitably a complex process for children in foster care for a number of reasons. The first is that services for children in care are highly variable across different localities (NICE, 2010) and tend to be delivered by a range of different agencies and professionals, including the local authority, CAMHS and the third sector. There is no comprehensive source of information regarding usual care for children in foster care in the UK in general, and less still about what treatments are offered to children with RAD. This makes it difficult to know what a usual care comparator in a trial would consist of, or how one might select appropriate research sites so that consistency in usual care can be assured. A second important challenge is the legal position of children in foster care, which complicates the process of gaining appropriate consents (Bogolub & Thomas, 2005). Third, as noted by the NICE guideline group (2015), there is a great deal of confusion in clinical practice regarding the diagnosis of RAD, which has tended to lead to poor identification of RAD in young children, and particularly over-reporting of RAD in older children ([name] & Scott, 2014). Among other things, this means that we cannot rely on referral systems to identify appropriate cases. Furthermore, in light of the relatively small numbers of young children in foster care (from 2014 DfE data 18% of children in England who were looked after for at least a year were aged 5 and under, averaging 56 cases per local authority) and the uncertainty regarding prevalence of RAD in this population we will work collaboratively with several local authorities to ensure adequate recruitment (both for a full trial but also for a pilot trial). Setting up such a collaborative system of case identification will be crucial for the success of the study. Finally, for a range of reasons, including the sometimes-precarious position of young children in foster care, stakeholders are understandably concerned to ensure that participating in research does not impact on their care and wellbeing. Examples of concerns that carers, parents or social workers may have include whether participation in treatment has implications for the likelihood of reunification, the relationship between the local authority and birth parents, or whether randomisation disadvantages some children in receiving appropriate treatment. Carers and practitioners may also express ethical concerns about the implications for a child of receiving a RAD diagnosis. In our initial discussions with foster carers and practitioners in the local authorities, all of these were raised as important issues for this study to address.

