#### Phase 3: Running a pilot RCT of modified VIPP-FC

The final phase of the study will consist of a pilot RCT, in which a new group of children with RAD (i.e., not those involved in the initial non-randomised clinical pilot series) will be randomised to receive VIPP-FC + Usual Care, versus Usual Care only. Children with RAD will be identified initially using a large community screening process in 6-10 local authorities to identify, at-source, children experiencing high levels of

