# **10** ANALYSIS

Feasibility parameters based on proportions (proportions of cases identified, consented, randomised, completing treatment and outcome measures). Approximate variance estimates will be obtained for the main outcome measures using the upper 80th percentile of the relevant confidence interval (see Brown, 1995). Specifically, we will test the following feasibility parameters:

A. Test the feasibility of identifying sufficient numbers of appropriate cases using screening instruments.

1. Target N for screening tests returned N = 500. Test a.1 = proportion and 95% CI of those returning screening instruments from total sent out.

2. Target N of diagnostic assessments N = 100. Test a.2 = proportion and 95% CI of positively screened cases (above upper 66th percentile) agreeing to full assessment.

3. Target N for positive diagnosis from upper 66th percentile of screened cases N = 50. Test a.3 = proportion and 95% CI of cases where diagnosis is confirmed.

4. Test a.4: initial test of false negative rate = proportion (of 25 cases) and 95% CI of detected diagnoses in random sample of cases not meeting screening threshold.

5. Initial non-parametric ROC curve analysis (total N = 125), based on assumption that DAI diagnosis is gold standard.

B. Test the feasibility of recruiting/consenting foster families with children with RAD to an RCT.

1. Target N of consented cases N = 40. Test b.1 = proportion and 95% CI of cases consenting to enter pilot trial from those meeting entry criteria.

C. Investigate feasibility of randomising to VIPP-FC or CAU.

1. Test c.1: proportion and 95% CI of cases accepting randomisation.

D. Document study throughput.

1. Test d.1: proportion and 95% CI of cases randomised completing treatment (definition of completing= 80% of offered sessions).

2. Test d.2: proportion of cases attending each session (6 proportions and 95% CIs).

4. Acceptability of treatment: means and ranges of client satisfaction survey. See also qualitative methods for client experience of treatment interviews.

E. Establish the feasibility and acceptability of baseline and outcome assessments.

1. Test e.1: proportion and 95% CI of cases with complete data. See also qualitative methods for client feedback regarding measures.

F. Identify the most appropriate primary outcome. Key assessment is participant feedback from qualitative interviews. However preliminary tests from H.2 below may also be informative.

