## 13.1 DELIVERABLES AND INDICATORS OF SUCCESS

For phase 1 of the study the key deliverable will be development of a new treatment (VIPP-FC) and the completion of a comprehensive treatment manual outlining clinical procedures for practitioners at each stage of treatment. This will have a potentially large impact on practice, as no evidence-based treatments currently exist for RAD, and treatment development in this area has been identified as a key health service priority (NICE, 2015; Wright et al., 2015). The initial success of this manual will be indicated by a) the feedback from practitioners and carers obtained in phases 2a and 3 regarding treatment delivery, b) feedback from practitioners during training, and b) feedback from the field through our dissemination activities. Phase 2a will yield a draft trial protocol based on experience of the feasibility case series, as well as refinements to the clinical manual. The findings of the case series will be published in a peer-reviewed journal. Phase 2b will end with the completion of a detailed report and research recommendations for trials of attachment interventions for children in foster care, to be published in a peer reviewed journal, as well as a final trial protocol for guiding the pilot trial in Phase 3 (which will also be published). The results of the pilot trial in phase 3 will produce vital data on the feasibility of a clinical trial of VIPP- RAD that will be used to plan a full-scale efficacy and health economic evaluation. The results of the pilot RCT will be published in a peer reviewed journal and disseminated to clinical and scientific conferences. This phase will yield definitive information about the feasibility of a future trial. Specifically, the following outcomes, were they to be identified by the project, would suggest that a full-scale trial should not proceed as currently configured: 1) inability to identify sufficient numbers of cases meeting diagnostic criteria for RAD, 2) inability to recruitment sufficient numbers of cases to enter treatment (e.g. due to problems with consent), 3) excessive placement instability and drop-out from the programme, 4) serious concerns about the acceptability of the treatment, randomisation or the outcome assessment battery raised by stakeholders. On completion of the study we will convene a group of stakeholders, including representatives of HTA, to consider whether a full trial should proceed, weighing up questions of scale (e.g., number of sites), design, cost and generalizability. Although thresholds for decisions about progression cannot all be determined in advance we consider that retention in treatment of < 70% would make a future trial non-viable. Similarly, an outcome assessment completion rate of < 70% would indicate non-progression. Although recruitment is less clear-cut, as sites can be added, an identification rate of RAD of < 10% would also lead to nonprogression.

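### Self-referred and agency-reached families enter the same screen as the mail-out, but the listed records omit route of entry and the screening yields are not separated by it

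*Protocol*

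**What the plan says.** Section 4.2 of the protocol (Phase 3) describes case finding as a population exercise: "Children with RAD will be identified initially using a large community screening process in 6-10 local authorities". Section 6.1 builds the recruitment funnel on about 700 foster children in the age range, a return above 80%, a working target of 500 screens, 150 children above the cut-off, 100 assessed and 50% of those with RAD.

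Section 6.2 (Screening and identification stage) gives three ways into the screen:

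- Mail-out: "all foster carers or special guardians registered with the local authority caring for children under 7 will be sent an information sheet", together with the screening measures and a consent form.
- Agencies: "Letters will also be sent to foster care agencies with information and contact details of the research team", which the agencies may hand on to their own carers.
- Self-referral: the sentence that begins "Where self-referrals are received, foster carers will be asked for" routes volunteers through the social worker, so that the authority starts the same process for them.

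Section 7.2 (Process Data and Qualitative Outcomes) lists what will be recorded about recruitment, including numbers approached and refusing, care orders, placement types and placement moves. Route of entry is not in that list.

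Section 10 defines test a.1 as the "proportion and 95% CI of those returning screening instruments from total sent out". Test a.2 is the share of screen-positive cases agreeing to assessment, and a.3 the share in whom the diagnosis is confirmed. None names a route. Section 13.1 adds that "an identification rate of RAD of < 10% would also lead to nonprogression", without giving a denominator. Sections 4.4 and 6.1 set a review after 15 assessed cases, also without reference to route.

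**The concern.** A carer who asks to be screened has already volunteered, and may well be looking after a child with more symptoms than the average mailed family. If so, every volunteer counted with the mailed families moves the confirmed-diagnosis and identification rates away from what a mail-out would yield. The protocol is itself wary of referral as a source of cases, saying in section 4.2 (Phase 2b) that "this means that we cannot rely on referral systems to identify appropriate cases".

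At stake is the use made of the pilot. Aim A is to show whether enough cases can be found through social care by screening, and the identification rate feeds a progression rule. A full trial planned on a combined rate could expect a yield per mailed carer that the mail-out does not produce. Route is also a data-capture item. If it is not noted when the screen comes in, a later analysis cannot reliably reconstruct it.

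**Working it through.** **1. The plan's own figures.** The section 6.1 funnel runs 500 screens → 150 above the cut-off → 150 × 2/3 = 100 assessed → 100 × 0.50 = 50 with RAD. The lower bound of 0.22 quoted for a proportion of 0.50 with 15 cases also reproduces, on a t-based interval: 0.50 − 2.145 × √(0.25/15) = 0.223. No figure in the protocol is wrong on this point.

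**2. What an identification rate could mean.** The funnel allows three denominators: 50/500 = 10%, 50/150 = 33% and 50/100 = 50%. Only the first puts the plan's own target exactly on the 10% line, so small shifts matter most there. Step 3 uses 500 as an assumption.

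**3. Effect on the 10% rule.** Let m be the mail-out rate, r the referred rate and s the referred share of a fixed 500 screens. The combined rate is m + s(r − m), so it reaches 10% when s = (0.10 − m)/(r − m). With m = 8% (assumed, just below the line):

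| Referred rate r (assumed) | Share s needed | Referred families in 500 | Check |
|---|---|---|---|
| 20% | 0.02/0.12 = 0.167 | 84 | (416 × 0.08 + 84 × 0.20)/500 = 10.0% |
| 35% | 0.02/0.27 = 0.074 | 38 | (462 × 0.08 + 38 × 0.35)/500 = 10.1% |
| 50% | 0.02/0.42 = 0.048 | 24 | (476 × 0.08 + 24 × 0.50)/500 = 10.0% |

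If r = m, nothing moves. If r < m, the combined rate falls.

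**4. Effect on a.1.** Take 500 returns from 700 sent, 71.4%, and add 25 referred returns (assumed). Counted in both numerator and denominator: 525/725 = 72.4%. Counted in the numerator only: 525/700 = 75.0%. The shift is about 1 to 4 points. For agency letters the number of carers reached is unknown, so the number sent out is not defined for that route.

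**5. Effect on a.3 and the 15-case review.** Both are taken among children above the screening cut-off, which referred children must also pass. With 3 of 15 assessed children referred, a mail-out rate of 15% and referred rates of 30%, 50% or 70% (all assumed), the combined rate is 18%, 22% or 26%. The chance of fewer than 3 diagnoses in 15 falls from 0.604 to 0.475, 0.312 or 0.166.

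**6. Steps 3 and 5 describe different populations.** Through the funnel, 15% among positives is 15/500 = 3% of screens, or 0.15 × 150/500 = 4.5% if every positive is assessed. Adding 40 referrals at 40% then gives (460 × 0.03 + 16)/500 = 6.0% to (460 × 0.045 + 16)/500 = 7.3%, so the 10% rule still fails. Conversely, 8% of 500 is 40 cases, which is 40/150 = 27% to 40/100 = 40% among positives. There the review triggers with probability only 0.19 to 0.03 even without referrals.

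**The case against.** The protocol nowhere says that the routes will be combined. A breakdown by route could sit in a screening form or an analysis plan that is not shown. That is fair: combination is what follows from applying sections 10 and 13.1 as written, not something the text announces. What stands is that the recruitment records are listed in some detail and route is not among them.

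Several stronger readings are tempting, and the document does not support them:

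- *A reader might infer that the return rate is badly inflated.* Test a.1 is tied to what was sent out, and step 4 shows a small effect.
- *A reader might infer that the 10% rule was set for the community population and is being evaded.* It has no stated denominator, section 13.1 notes that sites can be added, and a stakeholder group weighs progression.
- *A reader might infer that a few volunteers could both silence the 15-case review and carry the 10% rule.* Step 6 shows that these illustrations need incompatible prevalences.
- *A reader might infer that the review should use mail-out cases only.* It decides whether enough of the children actually being assessed meet criteria, so the mix being assessed is relevant to it.
- *A reader might infer that section 4.2 contradicts the use of referrals.* Its remark concerns poor identification and over-reporting of RAD in practice. Here self-referred children are still screened and their carers interviewed. Over-reporting could even lower the confirmed rate among them, so the direction is not established.
- *A reader might infer that the scoping question on supplementing the mail-out goes unanswered.* Section 4.2 answers it by interviews and documents, not by these counts.

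The routes may also overlap. A registered carer who self-refers has already been mailed, and agency letters may fill a gap in coverage. That lessens the bias, and is also a reason to know the route.

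**Conclusion.** The point holds as one of recording and reporting. Three routes feed one screen, the listed records do not distinguish them, and neither tests a.1 to a.3 nor the 10% rule separates them. If referred families carry more RAD, the combined diagnosis and identification rates overstate the community yield. On the assumption of 500 screens as denominator and an 8% mail-out rate, between 24 and 84 referred families would bring the rate to 10%, for referred rates from 50% down to 20%. Referral numbers and rates are all assumed, since the protocol gives none, and the shift vanishes if the two groups have equal rates. The return rate is little affected. The check does not show a wrong figure in the protocol, and it gives no ground for excluding referred children from the trial or from the 15-case review.

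**What to change.** - Add route of entry (mail-out, social worker, agency, self-referral) to the screening form and to the process data in section 7.2.
- Let eligible referred children enter as planned.
- Report a.1 to a.3 and the identification rate by route, with a.1 computed on mailed carers only.
- State the denominator of the 10% rule in section 13.1, and show the rule for mail-out children beside the all-route figure.
- Show the route mix when the 15-case review is read, without restricting that review to mail-out cases.

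The cost is one field and a few sentences. The mail-out figures rest on somewhat fewer children, so they are slightly less precise, and they may look less favourable. Recruitment is not restricted.

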### 5.5 Setting

This project is a multi-site collaboration between 3 universities, 5 NHS Trusts and linked local authorities and takes place across two large and distinctive regions in England, Greater London and the Yorkshire and Humber region. As noted already, a substantial number of local authorities is necessary to ensure adequate recruitment and to capture important variability in organisational contexts that will be important to understand when preparing a future larger-scale clinical trial. The identification of children in foster care with RAD will be supported by a screening mechanism run by the local authority in collaboration with the university. If necessary additional support will be offered to the Local Authorities to do follow-up phone calls to foster carers by a member of the local CRN or the research team with appropriate honorary contracts. Also, during routine appointments, social workers will seek verbal consent from foster carers to pass on their contact details to the research team so that they can contact them directly to follow-up completion and return of questionnaires. Once potential participants have been identified by the screening process and indicated their interest in taking part by returning the initial questionnaires and consent form or completing the online consent form and online questionnaires, the assessment of eligibility will be undertaken by the research team through an in-depth assessment conducted in the participants' homes. After randomisation the clinical intervention will be delivered by practitioners from one of the participating intervention teams. Below we provide further contextual information regarding each of the sites:

North East London Foundation NHS Trust (NELFT): NELFT provides care to a population of around 1.75 million people. The CAMHS services provide support for looked after children in the local authorities of Barking, Havering, Waltham Forest and Dagenham, and will shortly extend to Essex (providing scope for additional recruitment sites for this study if necessary). The research is strongly supported by the Interim Medical Director and its Research Director is a co-investigator ([name]). There are approximately 120 children in foster care under 7 (excluding Essex, which has a similar number).

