#### **Primary Outcome: Attachment Measure**

The Disturbances of Attachment Interview (DAI; Smyke & Zeanah, 1999) is a semi-structured interview to evaluate the presence of signs of disordered attachment (and is recommended by the NICE Guideline on attachment problems in children in care). For each of 12 sections, the interviewer asks multiple questions and follow-up probes sufficient to yield a rating reflecting degree of evidence of disturbed or disordered attachment: 0 = none/never, 1 = somewhat/sometimes, and 2 = considerable/frequently. The first five sections of the interview address signs of emotionally withdrawn/inhibited attachment disturbance (i.e. RAD), yielding total scores ranging from 0 to 10. The next three items address signs of indiscriminate behaviour, and the last four items address other signs of disturbances in attachment behaviour (known as 'secure base distortions'). There is sound evidence for the validity of this measurement system. First, it distinguishes between institutionalised and non-institutionalised children (Smyke, Dumitrescu, & Zeanah, 2002; Zeanah, Smyke, & Dumitrescu, 2002), reliably identifies signs of attachment disturbance in maltreated children (Zeanah et al., 2004) and validly distinguishes RAD from DSED (e.g., Oosterman & Schuengel, 2007). Second, it has shown very good interrater reliability (Oliveira, Fearon, Belsky, Fachada, & Soares, 2015) and high levels of internal consistency (Smyke et al., 2002; Zeanah et al., 2002). Third, criterion validity has been demonstrated through the convergence of attachment disorder diagnosis by different measurements. Construct validity has also been demonstrated by the association of DAI ratings with quality of care (e.g., Oliveira et al., 2005).

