#### **Broader impact measures**

• *Observed carer sensitivity*: We will use standardized observational procedures for assessing carer sensitivity during free play, and routine caregiving interactions (e.g., a snack, completing a challenging task). The interactions will be video-recorded, and scored blind to treatment condition and status (pre- versus post) by trained researchers. The scoring system used will be the Emotional Availability Scales, which have been extensively validated as indicators of interactions relating to attachment (Biringen, 2000). The interactions will be scored by a reliable coder (certified by the coding system developers). As in all our studies, interrater reliability will be tested on a proportion of cases (minimum 25%).

• *The Parent Stress Index* – Short Form (Abidin, 1990) will be used to assess carer wellbeing, strain and the carer-child relationship.

• *The Parenting Efficacy Scale* ([name] et al., 2012), a measure of beliefs and confidence about parenting skills.

• *Child and Adolescent Service Use Schedule* (CA-SUS; Barrett, Byford, Chitsabesan, & Kenning, 2006); assessing resource use for health economic evaluation.

• Practitioner feedback forms, to provide qualitative feedback about the experience of using VIPP in practice.

This battery of outcome assessments is similar to those we have used in other trials and cohort studies, and our previous experience is that it is not excessively burdensome. However, we will engage in extensive consultation with foster carers (through the carer advisory group) regarding acceptability and burden, and any changes recommend by that group will be implemented. Establishing the optimal balance between participant time /burden and the robustness of the outcome assessments is an important aim of this project as preparation for a full-scale trial.

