# 7.3 DATA MANAGEMENT

The data in this study will be collected and processed in accordance with the Data Protection Act (1998). Management of the data will be overseen by the Chief Investigator [name] with support from the Trial Coordinating Team. The case-series and pilot data will be collected by an experienced research assistant who has been trained to work with high-risk populations. The RA will be blind to treatment allocation, with all data issues related to unblinding being handled by the Trial Coordinating Team. Regular supervision with the Chief Investigator, Trial Coordinating Team and core study team (RAs) will ensure the reliability of data collection. Where necessary the RAs will be fully trained and certified in administering all research measures. For data that requires coding using standardized measures we will employ trained reliable coders, ensuring sufficient Inter-Rater Reliability (IRR) amongst coders.

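### The protocol does not blind the DAI interviewer to the screening result, so tests a.4 and a.5 and the item re-weighting are open to review bias that would flatter the screen

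*Protocol*

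**What the plan says.** **Route to interview (protocol 6.2, Screening and identification stage).** Screens come back to the research team by post or through the online database: once the "screening measures have been received by the research team, they will contact participants". Then: "Invitations and follow-up phone calls will be made to all foster carers reporting RAD symptoms over the screening cut-off". The stated purpose of the visit is to confirm eligibility by establishing diagnostic status. The section describes no invitation for carers below the cut-off.

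**Who diagnoses (5.5).** "the assessment of eligibility will be undertaken by the research team through an in-depth assessment".

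**Who collects and enters data (7.3, 7.4).** "The case-series and pilot data will be collected by an experienced research assistant". Section 7.4 has the research assistant transcribe the phase 3 paper forms into the database, and it counts the returned screening forms among the paper documents.

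**Blinding.** Section 7.3: "The RA will be blind to treatment allocation". The only other blinding stated is in 7.2, for the carer-sensitivity videos: "scored blind to treatment condition and status (pre- versus post) by trained researchers". Neither covers the screening result.

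**The reference standard (7.2).** In each DAI section "the interviewer asks multiple questions and follow-up probes sufficient to yield a rating" of 0, 1 or 2. Section 7.2 also says that the RAD diagnosis rests on the DAI rather than the DAWBA.

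**Its use (10, part A).** Test a.3 is the share of screen-positives with a confirmed diagnosis. Test a.4 is the share of diagnoses in 25 randomly sampled screen-negatives. Test a.5 is: "Initial non-parametric ROC curve analysis (total N = 125), based on assumption that DAI diagnosis is gold standard". Section 7.2 adds that screening item weights will be adjusted as full diagnostic assessments accumulate.

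**The concern.** When a judgement-based reference standard is rated by someone who knows the index-test result, the two tend to agree more than they should. An interviewer who expects RAD may probe further and resolve doubtful answers upwards. One who expects none may do the reverse. The effect is to confirm more screen-positives, find fewer cases among screen-negatives and raise the ROC area. All three favour the screen.

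Finding the best screening tool is a declared aim (4.2, Phase 3, item J; section 10, part H, which relies on a.4 and a.5). Because item weights are adjusted to the same diagnoses, any bias would also be built into the revised screen. It is systematic, so recruiting more children would not remove it.

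**Working it through.** **1. The plan's own numbers.** Section 6.1 expects 150 screen-positives among 500 screened, with two thirds assessed: 150 × 2/3 = 100. Half are expected to have RAD: 100 × 0.50 = 50, the target of a.3. Adding the 25 screen-negatives of a.4 gives 100 + 25 = 125, the N of a.5. The figures agree. The point is about conduct, not arithmetic.

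**2. What the interviewer could know, test by test.**

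| Test | Who is interviewed | What the text implies |
|---|---|---|
| a.3 | Screen-positives | Only carers over the cut-off have a route to interview in 6.2, so positive status is evident from the visit itself; the score need not be |
| a.4 | 25 screen-negatives | No route in 6.2, and nothing on whether the interviewer can tell them apart |
| a.5 | Both groups, N = 125 | Inherits both |

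The blinding in 7.3 concerns allocation, and randomisation follows the eligibility interview and baseline assessment (4.2, 6.3). It gives no protection at this visit.

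**3. Illustration by reclassification (assumed values, not in the protocol).** Suppose blind rating would find 50 cases in 100 screen-positives and 3 in 25 screen-negatives. Let knowledge of the screen turn a share b of the non-cases among positives into cases, and lose a share b of the cases among negatives.

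- Cases among positives: P = 50 + 50b
- Cases among negatives: M = 3(1 − b)
- Weights back to the 500 screened: 150/100 = 1.5 for positives and 350/25 = 14 for negatives
- Sensitivity = 1.5P / (1.5P + 14M)
- Specificity = 14(25 − M) / [1.5(100 − P) + 14(25 − M)]

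For b = 10%, P = 55 and M = 2.7. Sensitivity = 82.5 / (82.5 + 37.8) = 69%. Specificity = 312.2 / (67.5 + 312.2) = 82%.

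| b | a.3 | a.4 | Sensitivity | Specificity |
|---|---|---|---|---|
| 0% | 50% | 12.0% | 64% | 80% |
| 5% | 52.5% | 11.4% | 66% | 81% |
| 10% | 55% | 10.8% | 69% | 82% |
| 20% | 60% | 9.6% | 73% | 84% |

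**4. Illustration for the ROC area (also assumed).** Screen and severity are bivariate normal with correlation 0.5; the top 30% are screen-positive; the diagnostic threshold is set so that 50% of positives are cases. Ratings shift up by k in positives and down by k in negatives.

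| k (SD) | a.3 | a.4 | ROC area, 100 + 25 sample | ROC area, all screened |
|---|---|---|---|---|
| 0 | 50% | 19% | 0.69 | 0.74 |
| 0.1 | 54% | 16% | 0.70 | 0.77 |
| 0.2 | 59% | 14% | 0.72 | 0.80 |

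**5. Against sampling error.** The simulated standard deviation of the area at N = 125 is about 0.05, so a shift of up to about 0.04 is under one standard error. The exact 95% interval is 2.5–31.2% for 3/25 and 39.8–60.2% for 50/100. In step 3 the whole movement in a.4, from 3 to 2.4 expected cases, is less than one child.

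**The case against.** **The text does not say that the interviewer sees the screen.** This stands. A reader might infer that the interviewer works from the screening result and rates with knowledge of it. Section 6.2 shows who is invited, not what the interviewer is told. The protocol names a trial coordinating team apart from the research assistants, and the Gantt chart lists separate coordinator and trial assistant posts, so another person could score the screens. What the documents support is that nothing prevents the knowledge and the workflow makes it likely.

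**Silence is not an error.** This stands only in part. The protocol does fix the workflow, the route to interview and the assistant's blinding, and it names the DAI as the gold standard. Who knows what at a home visit is a matter of conduct, not something usually left to an analysis plan.

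**Test a.3 is meant to be unblinded.** This largely stands. It is the yield of a screen-then-interview pathway, in which the interviewer would ordinarily know that the child screened positive.

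**The decision rules are safe.** This stands as far as anything is shown. A reader might infer that the bias could distort the 15-case review (fewer than 3 of 15) or the non-progression rule (identification below 10%). From the planned 50%, a move to 54–59% is far from both triggers. If the rate is read as cases among all screened, the model in step 4 moves it slightly down, from about 28% to 27%.

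**Masking would be imperfect.** This stands. An interviewer would know that 100/125 = 80% of visits are to screen-positives. The carer both completes the screen and answers the DAI, so agreement from a shared informant remains whatever is masked.

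**Conclusion.** The point holds as a gap in protection. The protocol does not blind the DAI interviewer to the screen, routes only carers over the cut-off to interview, and leaves the 25 screen-negatives without a route. Tests a.4 and a.5 and the item re-weighting are open to review bias in the screen's favour; a.3 is affected less.

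The direction follows from the design if the interviewer knows the status. The size does not: the prevalences, the correlation of 0.5, and the shifts and shares in the illustrations are all assumptions. Under them the effect on the planned sample is small beside its sampling error. Neither actual knowledge of the result nor a changed progression decision is established. This is a cheap improvement worth making, not a flaw that undermines the pilot.

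**What to change.** **Section 6.2**
- A member of the trial coordination team, not the interviewing research assistant, receives, scores and enters the screens. This includes the database notifications for online returns.
- Add an invitation route for the 25 randomly sampled screen-negatives.
- Issue visits in rolling batches that mix positives and negatives, without scores or status. Batches suit screens that return over a 12-month recruitment period.
- The research assistant locks the DAI rating before screen status is released.

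**Section 7.4**
- Bring the sentence on transcription of paper forms into line with this.

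**Section 10**
- State that a.4 and a.5 use DAI ratings made without access to the screen.
- Report as a limitation that masking is partial, because about 80% of those interviewed are screen-positive.

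**Cost.** A few protocol sentences and some scheduling work, using posts that already exist. The sample sizes of 100, 25 and 125 do not change. This protocol version is dated January 2019 and its timetable ends recruitment in February 2019, so some interviews may already be done. For those, the report should say whether the interviewer knew the screening result.
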